**Number of Subjects:**

We intend to enroll a total of 24 volunteers. This will allow for n=20 to complete the study, conservatively assuming 20% total attrition rate.

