**Study Design:**

Patients with recent, unilateral ACL rupture or combined ACL rupture/meniscus injury, who are undergoing surgical reconstruction, will be recruited and randomized to active NMES or control (placebo) interventions, with stratification for age, sex and graft type (knee extensor autograft, knee flexor autograft or allograft). All personnel performing assessments on patients/tissue will be blinded to group assignment. A within-subject design will be used, where the injured, surgically-treated leg will be compared to the contralateral, uninjured leg. NMES or control interventions will begin shortly following injury (within 3 wks) and run till 3 wks post-surgery. Patients will be evaluated twice pre-surgery and then at 3 wks and 6 mos post-surgery. There is the possibility for an additional visit prior to Pre-Surgery Testing #1 to assure that we consent volunteers and start the NMES/control intervention prior to 3 week post-injury. We will make every attempt to limit this

**Pre-surgery testing #1** (within 3 wks of injury) will consist of clinical/patient-oriented assessments (IKDC, KOOS) and functional testing (uninjured leg only).

**Consent/Device Training Visit** will occur within 3 wks of injury to begin the NMES/control intervention if the Pre-surgery testing #1 visit cannot be scheduled within this time constraint. Volunteers will be consented and will undergo training in the use of the NMES or control intervention (detailed below).

**NMES/Control intervention** will begin within 3 wks of injury following pre-surgery testing, with patients randomized (1:1). Active NMES intervention will consist of active NMES 5 d per week, with each session lasting 60 min. For the control intervention, volunteers will receive a sham NMES device to maintain blinding and will be told that they will receive imperceptible, microcurrent stimulation for pain mitigation. In the sham device, electrical leads are disconnected so that no current can leave the NMES device.

**Pre-surgery testing #2** (~1 wk pre-surgery) will be identical to Pre-surgery #1 testing, but will include strength testing of the injured leg.

Post-surgery testing #1 (3 wks) will consist of bilateral muscle biopsies for cellular structure and function measures and bilateral thigh muscle size assessments.

Standardized rehabilitation will begin 3 wks post-surgery, with both groups undergoing the same accelerated rehabilitation program that is standard of care within our practice.

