To obtain data to estimate samples sizes based on these relative differences, we used a larger data set of knee OA patients (n=16) assessed for identical measurements proposed in this application (single fiber CSA and function). Mixed linear models were developed to estimate both between cluster variances and intraclass correlation coefficients (ICC), where samples were obtained at times before and after treatment, with clusters of fibers available for each volunteer at each time point. Cluster variance and ICC estimates were 1,030,622 and 0.337 for MHC I CSA; 1,047,066 and 0.383 for MHC II CSA; 254 and 0.263 for MHC IIA tension and 576 and 0.610 for MHC IIA velocity, respectively. These data were then used in a two group repeated measures analysis of variance model to estimate power for group, leg and group X leg interaction effects. Using relative differences detailed above and variance estimates from our mixed model analyses, we estimated that an n=10/group would detect significant group X leg interaction effects for MHC I CSA and MHC IIA tension and velocity, with powers in excess of 80% (87%, 99% and 99%, respectively) at a significance level of 5%. We chose these three variables because they represent important determinants of whole muscle size and function. More specifically, as the most prevalent fiber type in muscles (3, 4), MHC I CSA is the most important factor determining whole muscle size. Similarly, given that MHC IIA fibers are the most prevalent fast-twitch, type II fiber in human muscle, it disproportionately determines the contractile characteristics of whole muscle because of its large power output (2, 5). Power output is dependent on both the force producing capacity and contractile velocity of the constituent fibers (ie, power=force X velocity). Thus, we have included both force and velocity in our sample size estimates. Of note, we did not focus on MHC IIAX fiber function because, unlike our studies in older adults, where these fiber types are much more prevalent, far fewer of these fibers are present in younger adults (4), who will comprise the majority of our ACL injured population. Assuming ~20% dropout rate, based on our prior work (6-8), we will enroll 12 individuals/group with the expectations of a final sample size of 10/group.

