In Aim 2, our primary outcome is knee extensor isokinetic torque. Using our data in ACL reconstructed patients (Fig 1), we anticipate reductions in isokinetic muscle strength at 6 months post-surgery of -30% vs. uninjured leg in volunteers randomized to the control group (10). Given the effect of NMES to prevent atrophy and contractile dysfunction at the cellular level (Fig 2) and preliminary evidence from others showing that NMES maintains whole muscle size and strength post-surgery (11), we predict that loss of isokinetic strength will be minimal at 6 months (~5% loss or 95% of uninjured) in the NMES group. Based on these differences, a sample of n=10/group would detect a group X leg interaction effect with 80% power and a significance level of 0.05. We have not performed sample size estimates on secondary outcome variables, as it is unlikely that our sample size and length of follow-up will be sufficient to detect effects of NMES on these factors. In anticipation of observing salutary effects of NMES on muscle size and function (Aim 1), analyses of these secondary outcome variables will provide preliminary data to inform power calculations for future randomized controlled clinical trials to interrogate broader clinical efficacy of NMES to mitigate skeletal muscle structural and

functional adaptations to traumatic knee injury and surgical intervention, with the goal of mitigating long-term knee pathology (10).

Statistical analytical approach: Our primary goal is to assess the effect of group assignment (NMES vs. control) on skeletal muscle fiber size and contractile function 3 wks post-surgery using a mixed model, with group and leg (injured vs. non-injured) as fixed effects and subject ID and fiber number as random effects to account for the pairing of legs and clustering of fibers within each volunteer, respectively, as generally described (21). Primary outcomes include: MHC I and II fiber CSA and MHC IIA tension (force/CSA) and velocity. Any confounding factors differing between groups (eg, physical activity level, time between injury and surgery, tourniquet time during surgery) can be included as covariates, although most factors should be balanced by randomization.

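### At the stated 20% attrition, 24 enrolled leave an expected 19.2 completers (9.6 per group), slightly short of the 20 (10 per group) at which every power is stated

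*Protocol*

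**What the plan says.** The protocol, under Number of Subjects, gives the enrolment: "We intend to enroll a total of 24 volunteers". It continues: "This will allow for n=20 to complete the study, conservatively assuming 20% total attrition rate". The rate there carries no qualifier.

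The SAP, under Sample size estimates, gives the matching per-group figures. The rate is approximate and tied to earlier studies: "Assuming ~20% dropout rate, based on our prior work (6-8"). From it, "we will enroll 12 individuals/group with the expectations of a final sample size of 10/group". Allocation is 1:1 (protocol, Study Design).

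Every stated power refers to that final size. For Aim 1, "we estimated that an n=10/group would detect significant group X leg interaction effects for MHC I CSA and MHC IIA tension and velocity". The SAP puts the power for these three outcomes at 87%, 99% and 99% in turn, testing at the 5% level. For Aim 2, "a sample of n=10/group would detect a group X leg interaction effect with 80% power and a significance level of 0.05".

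Neither document gives another attrition rate, or a plan to over-enrol or replace those who leave.

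**The concern.** The enrolment, the attrition rate and the number of completers do not fit together. If 20% are lost, fewer than 20 of 24 are expected to finish. If 20 of 24 finish, fewer than 20% were lost. The likely cause is a common slip: multiplying the required number by 1 + d instead of dividing it by 1 - d.

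All four powers are tied to 10 per group. Aim 2 is quoted at 80%, so any shortfall takes it below that level. Its outcome is measured at 6 months, the last visit, when total attrition applies in full. The SAP also says the secondary outcomes will inform power calculations for later trials, so the attrition method should be right before it is reused.

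**Working it through.** **Inputs.** Enrolled: 24 in total, 12 per group. Completers: 20 in total, 10 per group. Attrition d: 20% in the protocol, about 20% in the SAP. Powers at 10 per group: 87% (MHC I CSA), 99% (MHC IIA tension), 99% (MHC IIA velocity) and 80% (Aim 2 torque). The significance level is 5%. Sidedness is not stated, so two-sided is assumed.

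**1. Reproducing the plan's 24.**
- N x (1 + d) = 20 x 1.2 = 24, or 10 x 1.2 = 12 per group. This matches exactly.
- N / (1 - d) = 20 / 0.80 = 25. Per group, 10 / 0.80 = 12.5, so 13 per group and 26 in total for equal groups.

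**2. What 24 delivers.**
- At 20% loss: 24 x 0.80 = 19.2, or 12 x 0.80 = 9.6 per group. The shortfall is 20 - 19.2 = 0.8 of a participant.
- Loss implied by 24 to 20: 4 / 24 = 16.7%.

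**3. Effect on power (approximate).** Power cannot be rebuilt directly. The effects are percentages, the variances are in absolute units with no baseline means, and Aim 2 has no SD. I therefore took a two-sample t-test on the within-person leg difference, found the standardised effect that gives each stated power at 10 per group, and recomputed at smaller sizes. Power = P(T > t(0.975, df)), with T noncentral t, df = n1 + n2 - 2 and noncentrality = effect / sqrt(1/n1 + 1/n2).

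| Stated power at 10/10 | Back-solved effect | 9.6/9.6 | 10/9 | 9/9 |
|---|---|---|---|---|
| 80% (Aim 2) | 1.325 | 78.2% | 77.6% | 75.1% |
| 87% (MHC I CSA) | 1.460 | 85.5% | 84.9% | 82.8% |
| 99% (tension, velocity) | 2.030 | 98.7% | 98.6% | 98.1% |

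A normal approximation at 9.6 per group gives 78.4%, 85.6% and 98.7%.

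**4. Chance of reaching the stated size.** This assumes independent dropout. The right-hand column is the baseline at which 24 to 20 is correct on average.

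| Event | 20% loss | 16.7% loss |
|---|---|---|
| At least 20 of 24 complete | 46% | 63% |
| At least 10 complete in both groups | 31% | 46% |

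Much of the risk of missing 20 is chance variation, which would remain with the arithmetic corrected. The error accounts only for the difference between the columns.

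**The case against.** The case for leaving the text alone has several parts.

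- **Size.** The gap is 0.8 of a participant. The SAP's approximate 20% could loosely cover 16.7%, and 9.6 rounds to 10. This stands for the SAP, but not for the protocol, where the rate is unqualified.
- **Timing for Aim 1.** The protocol's rate is total attrition to study completion at 6 months, while the Aim 1 biopsies are taken 3 weeks after surgery. Anyone lost between those points still contributes to Aim 1. This stands in part: the recomputed Aim 1 power is a lower bound if some loss comes later. However, the SAP itself sets the dropout allowance against the 10 per group used for Aim 1, and no 3-week rate is given.
- **Precision.** The recomputed powers start from rounded figures and an assumed two-sided test. This stands. They are approximations, and a quoted 80% does not show that the sponsor's calculation had no margin.
- **The word *conservatively*.** A reader might infer that the protocol calls 24 a conservative size, which would be wrong in direction. The sentence can equally mean that 20% is a cautiously high rate. The prior work that would settle this is cited but not reproduced, so the documents do not establish a false claim, only an unclear one.
- **Usefulness.** The protocol's section on information withheld from subjects already describes participation in the past tense, so enrolment planning may be largely over. This argues for correcting the text, not the number enrolled.

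**Conclusion.** The point holds as a minor arithmetic error in a stated size. At 20% attrition, 24 enrolled give an expected 19.2 completers, not 20. That much needs no assumption beyond the plan's own figures.

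The consequence for power is small and approximate: about 78% instead of 80% for Aim 2, and about 85% instead of 87% for MHC I CSA. Tension and velocity stay near 99%. These figures rest on back-solved effects, a two-sided 5% two-sample t-test on the leg difference, and the full 20% loss applying to each outcome.

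A reader might infer that the primary aim is underpowered. This calculation does not support that: taking the SAP's powers as given, the Aim 1 outcomes it quotes stay above 80% even at 9 per group. A reader might also take the 46% and 31% completion probabilities as the cost of the error. They are not, since the corresponding values are only 63% and 46% when the arithmetic is right.

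**What to change.** Keep 24 enrolled and correct the sentence in the protocol's Number of Subjects and its counterpart in the SAP's Sample size estimates, in one of two ways:

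1. State that 24 enrolled (12 per group) allows about 17% attrition for 20 completers, and drop *conservatively* or make clear what it describes.
2. Keep 20%, state about 19 expected completers, and restate the powers from the sponsor's own means, SDs and model. The figures of about 78% and 85% above show the order of change and should not be copied in as the result. If dropout before the 3-week biopsy is expected to be lower than total dropout, give that rate for Aim 1.

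If completion probabilities are quoted, show them at both 20% and 16.7% loss.

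The cost is one sentence in each document, plus a rerun of the power calculation under the second option. No participants are added, and the design, outcomes and analysis do not change. Under the second option the stated power becomes slightly less favourable.

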**Inclusion/Exclusion Criteria:**

Patients (50:50 men-women) will be included if they are/have: 1) 18-50 yrs; 2) BMI <35 kg/m^2; 3) acute, first-time, ACL rupture with or without meniscus injury and 4) scheduled to undergo reconstruction with any type of autograft or allograft. Patients will be excluded if they are/have: 1) history of prior knee/lower extremity surgery or non-surgical intervention (eg, intra-articular injection) on either leg; 2) abnormal laxity of any lower extremity ligament other than the injured ACL; 3) signs or symptoms of arthritis, autoimmune or inflammatory disease or diabetes; 4) grade IIIb or greater articular cartilage lesions (ICRS criteria) and/or 5) women who are/plan on becoming pregnant.

**Inclusion of Minorities and Women:**

Inclusion of Women

This study will include equal numbers of men and women.

Inclusion of Minorities

Every effort will be made to recruit minorities for the proposed studies. The contribution of minorities

to the total population of Vermont is 3.2%, with a similar minority profile in Chittenden County (3.6%), where the University of Vermont (UVM) is located.

***Inclusion of Children:***

The proposed studies will not include children. The rationale for this decision is based on the fact that children are a vulnerable population and it could be argued that performance of the invasive procedures proposed in these studies, such as muscle biopsies, would not be justified without proven efficacy of the NMES intervention. Based upon the Belmont Report (Part C, §3), there is an order of preference for performing research on volunteers, which stipulates that in research that does not have a known therapeutic value, or by extrapolation to the proposed studies, where the utility of the therapeutic intervention is in question, that those less burdened populations should be called upon first to accept the risks of research. In the context of this criterion, this would mean that adults be studied before children. Traumatic knee injury is indeed relevant to children, as a fraction of patients experience this injury in their late teenage years. However, we believe that it is prudent to first investigate the utility of NMES in the adult population before it is evaluated in children. If our studies are successful, we would anticipate that future randomized, controlled trials evaluating the efficacy of NMES to improve current rehabilitation strategies for recovery from traumatic knee injury and surgical repair would include children.

***Recruitment:***

Patients will be recruited from the Sports Medicine service of the UVMMC Department of Orthopedics and Rehabilitation. Additionally, because we have to identify volunteers within 3 week of injury, we will also receive referrals to our research group from other local clinical practices, local universities and University student health offices who have a suspected ACL rupture. These clinical practices will document patient's interest in the study and consent to have their contact information sent to our research team.

***Consent Procedures:***

Someone with a treatment relationship will introduce the study to potential volunteers (UVMMC Department of Orthopedics and Rehabilitation, EMRAP, athletic trainers at local universities). If the patient expresses interest in the study and would like more information about the study, the research coordinator or PI will contact the volunteer, explain the study and will provide a copy of the informed consent. The PI and/or the research coordinator will answer any questions by phone or in person. Moreover, the PI or the research coordinator will discuss the protocol with the volunteer at length and answer any remaining questions.

***Information Withheld From Subjects:***

Volunteers randomized to the sham, microcurrent stimulation group will not be told that the device that they receive was modified to emit no electrical current. This deception is necessary so that we can achieve a proper sham intervention, which was requested by the NIH review group. The review group was concerned that the volunteer's knowledge of no intervention (if we had a standard of care control with no sham device being used) would affect their efforts on volitional tests, such as strength testing (secondary aim) and functional testing, or their report of quality of life and knee pain/function on questionnaires. The latter measurements were of particular concern, as the committee considers these metrics essential for future randomized controlled trials to test the efficacy of NMES in this patient population. Thus, they felt that a sham device was needed to eliminate bias. We will debrief volunteers at the completion of the study regarding this deception.

For debriefing of volunteers randomized to the sham control group, we will contact volunteers by phone to schedule a time to provide them with the Debriefing Form and explain the deception and sign the Debriefing Form. There is also a place on the form for volunteers to check "Yes" or "No" as to whether we may use their data. Many of the volunteers were students. Some of them have moved out of the area since their participation in the study. In these volunteers, we will try to contact them via phone, text or email to debrief them verbally. In this event, study personnel will use a script that mirrors the points noted in the debriefing memo. This Script will also be used to document the volunteers assent/decline to assent, as well as the date of the contact and, for those patients who we cannot contact, these dates of attempts to contact. We will provide the volunteers with a copy of the Debriefing Form and obtain their signature after the phone conversation. For those volunteers who we cannot contact, we will attempt to contact them two (2) times. Any volunteer who cannot be contacted for debriefing will be noted in the Continuing Review.

Official Title: *Prevention of Skeletal Muscle Adaptations to Traumatic Knee Injury and Repair*

NCT: NCT02945553

Document date: 2 July 2019

STATISTICAL ANALYSIS PLAN

Sample size estimates: A primary goal of the proposed studies is to demonstrate, using measurements at cellular and sub-cellular levels, that early institution of NMES prevents deterioration in skeletal muscle fiber size and function in patients with traumatic knee injury throughout the post-injury and early, post-surgical periods. In Aim 1, primary outcomes consist of: 1) single muscle fiber cross-sectional area (CSA)(MHC I and II fibers), 2) tension (MHC I and IIA fibers) and 3) velocity (MHC I and IIA fibers). In calculating samples size estimates for single fiber measurements, we assume that, for each patient, ~200 fibers will be evaluated for single muscle fiber CSA, with the goal of obtaining 100 MHC I and 100 MHC II fibers and ~25-30 fibers for mechanical assessments, with the goal of obtaining 10 MHC I and 10 MHC IIA fibers. The remaining fibers assessed for mechanical measures will likely be comprised of mixed MHC isoform fibers (IIA/IIX) and will be too few for analysis without analyzing prohibitively large numbers of fibers/patient. These fibers also constitute a relatively small fractional percentage of the total number of fibers in patients. Our estimates for relative changes in single muscle fiber CSA and function are based on data from our laboratory and others at the single fiber (1) and whole muscle (2) levels in patients experiencing ACL rupture and reconstruction, as well as data from our laboratory in another orthopedic surgical population (Fig 2). From these data, we expect reductions at 3 weeks post-surgery in single fiber CSA of -30% and -40% for MHC I and II fibers (Fig 2), respectively, and in tension (-50%) and velocity (-30%) in MHC IIA fibers (Fig 2), in patients randomized to control treatment. Based on our observed effects of NMES (Fig 2) to mitigate muscle fiber atrophy and dysfunction in total knee arthroplasty (TKA) patients, we estimate that reductions in these variables will be prevented or diminished (CSA: 0% and -10% for MHC I and II fibers, respectively; tension in MHC IIA fibers: -40%; velocity in MHC IIA fibers: +20%).

To obtain data to estimate samples sizes based on these relative differences, we used a larger data set of knee OA patients (n=16) assessed for identical measurements proposed in this application (single fiber CSA and function). Mixed linear models were developed to estimate both between cluster variances and intraclass correlation coefficients (ICC), where samples were obtained at times before and after treatment, with clusters of fibers available for each volunteer at each time point. Cluster variance and ICC estimates were 1,030,622 and 0.337 for MHC I CSA; 1,047,066 and 0.383 for MHC II CSA; 254 and 0.263 for MHC IIA tension and 576 and 0.610 for MHC IIA velocity, respectively. These data were then used in a two group repeated measures analysis of variance model to estimate power for group, leg and group X leg interaction effects. Using relative differences detailed above and variance estimates from our mixed model analyses, we estimated that an n=10/group would detect significant group X leg interaction effects for MHC I CSA and MHC IIA tension and velocity, with powers in excess of 80% (87%, 99% and 99%, respectively) at a significance level of 5%. We chose these three variables because they represent important determinants of whole muscle size and function. More specifically, as the most prevalent fiber type in muscles (3, 4), MHC I CSA is the most important factor determining whole muscle size. Similarly, given that MHC IIA fibers are the most prevalent fast-twitch, type II fiber in human muscle, it disproportionately determines the contractile characteristics of whole muscle because of its large power output (2, 5). Power output is dependent on both the force producing capacity and contractile velocity of the constituent fibers (ie, power=force X velocity). Thus, we have included both force and velocity in our sample size estimates. Of note, we did not focus on MHC IIAX fiber function because, unlike our studies in older adults, where these fiber types are much more prevalent, far fewer of these fibers are present in younger adults (4), who will comprise the majority of our ACL injured population. Assuming ~20% dropout rate, based on our prior work (6-8), we will enroll 12 individuals/group with the expectations of a final sample size of 10/group.

In Aim 2, our primary outcome is knee extensor isokinetic torque. Using our data in ACL reconstructed patients (Fig 1), we anticipate reductions in isokinetic muscle strength at 6 months post-surgery of -30% vs. uninjured leg in volunteers randomized to the control group (10). Given the effect of NMES to prevent atrophy and contractile dysfunction at the cellular level (Fig 2) and preliminary evidence from others showing that NMES maintains whole muscle size and strength post-surgery (11), we predict that loss of isokinetic strength will be minimal at 6 months (~5% loss or 95% of uninjured) in the NMES group. Based on these differences, a sample of n=10/group would detect a group X leg interaction effect with 80% power and a significance level of 0.05. We have not performed sample size estimates on secondary outcome variables, as it is unlikely that our sample size and length of follow-up will be sufficient to detect effects of NMES on these factors. In anticipation of observing salutary effects of NMES on muscle size and function (Aim 1), analyses of these secondary outcome variables will provide preliminary data to inform power calculations for future randomized controlled clinical trials to interrogate broader clinical efficacy of NMES to mitigate skeletal muscle structural and

functional adaptations to traumatic knee injury and surgical intervention, with the goal of mitigating long-term knee pathology (10).

Statistical analytical approach: Our primary goal is to assess the effect of group assignment (NMES vs. control) on skeletal muscle fiber size and contractile function 3 wks post-surgery using a mixed model, with group and leg (injured vs. non-injured) as fixed effects and subject ID and fiber number as random effects to account for the pairing of legs and clustering of fibers within each volunteer, respectively, as generally described (21). Primary outcomes include: MHC I and II fiber CSA and MHC IIA tension (force/CSA) and velocity. Any confounding factors differing between groups (eg, physical activity level, time between injury and surgery, tourniquet time during surgery) can be included as covariates, although most factors should be balanced by randomization.

The goal of this analysis is to determine whether dynamic muscle strength is better preserved in the injured limb in the NMES group compared to controls 6 mos post-surgery. As in Aim 1, a mixed model will be used, with group and leg effects and subject ID as a random effect. As strength in the injured leg will be compared to the contralateral, uninjured leg, we will monitor strength in the contralateral leg throughout the study (Fig 3) to use as a covariate if any group differences are found. Other covariates that may differ between groups include crutch use, compliance with rehabilitation/activity restrictions and time between injury and surgery. Secondary analysis will evaluate changes in SLH, quadriceps muscle CSA, JSW, MRI outcomes and KOOS, SF-36 and IKDC scores.

References

2. Callahan, D. M., Miller, M. S., Sweeny, A. P., Tourville, T. W., [name], J. R., Savage, P. D., Maughan, D. W., Ades, P. A., [name], B. D., and [name], M. J. (2014) Muscle disuse alters skeletal muscle contractile function at the molecular and cellular levels in older adult humans in a sex-specific manner. *J Physiol* 592, 4555-4573
3. Callahan, D. M., Tourville, T. W., Miller, M. S., Hackett, S. B., Sharma, H., Cruickshank, N. C., [name], J. R., Savage, P. D., Ades, P. A., Maughan, D. W., [name], B. D., and [name], M. J. (2015) Chronic disuse and skeletal muscle structure in older adults: sex differences and relationships to contractile function. *Am J Physiol Cell Physiol* 308, C932-C943
4. Miller, M. S., Bedrin, N. G., Callahan, D. M., Previs, M. J., Jennings, M. E., Ades, P. A., Maughan, D. W., Palmer, B. M., and [name], M. J. (2013) Age-related slowing of myosin actin cross-bridge kinetics is sex specific and predicts decrements in whole skeletal muscle performance in humans. *J Appl Physiol* 115, 1004-1014

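### Both aims are powered on group × leg, but neither analysis model contains that term or names the NMES test, and the Aim 1 model names no biopsy effect

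*SAP*

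**What the plan says.** **Sizing.** For Aim 1, the SAP (Sample size estimates) uses a two-group repeated-measures model to "estimate power for group, leg and group X leg interaction effects". It reports that 10 per group "would detect significant group X leg interaction effects for MHC I CSA and MHC IIA tension and velocity", with powers of 87%, 99% and 99%. For Aim 2 it says that "a sample of n=10/group would detect a group X leg interaction effect with 80% power". The variance inputs came from knee osteoarthritis patients, "with clusters of fibers available for each volunteer at each time point".

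**Analysis.** Under Statistical analytical approach, the Aim 1 model is described "with group and leg (injured vs. non-injured) as fixed effects and subject ID and fiber number as random effects". Subject ID is there for the pairing of legs and fiber number for the "clustering of fibers within each volunteer, respectively, as generally described (21"). The SAP reference list ends at 12. The Aim 1 objective is worded as the effect of group assignment. For Aim 2, "a mixed model will be used, with group and leg effects and subject ID as a random effect"; the stated goal is to learn "whether dynamic muscle strength is better preserved in the injured limb in the NMES group compared to controls".

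**Design.** The protocol takes a biopsy from each leg at 3 weeks (Procedures, Primary Aim), stimulates only the injured leg (Interventions), and uses the other leg as the within-subject control (Subject Selection).

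**The concern.** There are two separate gaps.

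1. **Both aims: no interaction term and no named test.** The sizing text treats group, leg and group × leg as three separate items, so a model sentence that lists only group and leg does not plainly include the third. In the model as listed, the only NMES coefficient is the group main effect, averaged over a stimulated and an unstimulated leg.
2. **Aim 1 only: no term for the biopsy.** Fibres are nested in leg within volunteer. A subject intercept is shared by both legs and cancels from the injured-minus-uninjured contrast. Unless something represents leg within subject, the interaction is judged against fibre-to-fibre variation, and many fibres from one biopsy count as independent evidence.

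At stake is the primary test of both aims. An analyst who follows the text literally tests a halved effect. One who adds only the interaction may report Aim 1 p-values that are far too small. Both could claim to have followed the SAP.

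**Working it through.** **The plan's own powers.** These can be neither confirmed nor refuted. The uninjured-leg means (Aim 1) and the SD of torque (Aim 2) are not given. Solving backwards on 18 df, two-sided 5% (sidedness assumed), 87% for MHC I CSA needs an uninjured-leg mean of about 980–1,390 if all cluster variance is between subjects, 5,040–5,130 if half is leg-specific, and 7,060–7,120 if all is. The 80% for torque implies an SD of the leg difference of about 18.9 points. The stated powers are taken as true below.

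**Inputs from the SAP.** Cluster variance V and ICC: MHC I CSA 1,030,622 and 0.337; MHC II CSA 1,047,066 and 0.383; MHC IIA tension 254 and 0.263; MHC IIA velocity 576 and 0.610. n = 10 per group. Target fibre counts of each type are given per patient (100 for CSA, 10 for mechanics), so m, the fibres per leg, is taken as 50–100 or 5–10.

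**Assumed.** A share s of V is specific to the leg and 1−s is common to the subject. The SAP gives no split, so s is varied.

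**Within-cluster variance.** W = V(1−ICC)/ICC gives 2,027,604 (MHC I CSA), 1,686,788 (MHC II CSA), 711.8 (tension) and 368.3 (velocity).

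**(a) Model as listed: group main effect.** With no NMES effect in the uninjured leg, the planned differences halve:
- MHC I CSA: 0 − (−30) = 30 points, to 15
- MHC II CSA: −10 − (−40) = 30, to 15
- MHC IIA tension: −40 − (−50) = 10, to 5
- MHC IIA velocity: 20 − (−30) = 50, to 25
- Torque: −5 − (−30) = 25, to 12.5

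The correlation of the two leg means is ρ = (1−s)V/(V + W/m). The interaction contrast has variance proportional to 2(1−ρ); the subject average has (1+ρ)/2. With the effect halved, the noncentrality is multiplied by √[(1−ρ)/(1+ρ)]. The noncentralities for 87%, 99% and 80% on 18 df are 3.265, 4.540 and 2.963.

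Example, MHC I CSA, s = 0.25, m = 100: ρ = 772,967/1,050,898 = 0.736; multiplier √(0.264/1.736) = 0.390; 3.265 × 0.390 = 1.27; power 23%.

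Power of the group main effect (range over m):

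| s | MHC I CSA | Velocity | Tension |
|---|---|---|---|
| 0.1 | 12–13% | 24–30% | 43–60% |
| 0.25 | 23–24% | 43–49% | 59–72% |
| 0.5 | 44–45% | 73–76% | 81–87% |
| 1 | 87% | 99% | 99% |

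MHC II CSA has no stated power, so none is derived. For torque, power is 80%, 58% and 37% at assumed leg correlations of 0, 0.25 and 0.5. The type I error of this test stays near 5%.

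**(b) Interaction added, no biopsy effect (fiber number as residual or arbitrary label).** The subject-by-leg mean square exceeds the fibre mean square by λ = 1 + m·s·V/W. The test divides the group × leg mean square by a pooled error on 18 + 40(m−1) df (40 = 20 subjects × 2 legs).

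Example, MHC I CSA, s = 0.5, m = 100: λ = 1 + 50 × 1,030,622/2,027,604 = 26.4; pooled error (18 × 26.4 + 3,960)/3,978 = 1.115; the SE is understated by √(26.4/1.115) = 4.9.

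Rejection rate under the null, nominal 5% (400,000 simulated trials per setting):

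| s | MHC I CSA | MHC II CSA | Velocity | Tension |
|---|---|---|---|---|
| 0 | 5% | 5% | 5% | 5% |
| 0.1 | 29–42% | 33–46% | 13–20% | 7–9% |
| 0.25 | 46–59% | 49–62% | 21–33% | 10–14% |
| 0.5 | 58–69% | 61–71% | 30–44% | 14–22% |

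With a biopsy effect and 18 df, a separate simulation gave 4.8–5.1%.

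**The case against.** **The interaction is clearly intended.** The power text, the within-subject design and the worded Aim 2 goal all point to it, and listing the factors could be shorthand for the factorial model just sized. The intent is accepted. But the Aim 1 objective is worded as the effect of group assignment, which matches the main effect, and inferring a test is not pre-specifying it.

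**Fiber number is meant to handle clustering.** A residual or arbitrary label could not do that, and the sizing clusters were per biopsy, so the authors may have meant a biopsy index. If so, the second fault is absent. But the text speaks of clustering within the volunteer, not the leg, and the method is deferred to a reference that is not in the list. What is shown is ambiguity with a bad outcome under one reading.

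**The two harms need different readings.** This is correct; they do not add. Power loss is largest when a person's legs are alike, inflation when they differ, so the extremes cannot coincide.

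**Fixing 87% while s varies moves the implied mean.** This also stands: much of the gradient in table (a) reflects the changing mean rather than leg similarity. Holding the MHC I CSA mean fixed (m = 100), main-effect power at s = 0.1, 0.25 and 0.5 is 12%, 13% and 14% at a mean of 2,417, and 37%, 39% and 45% at 5,085. A correctly specified interaction test has 87%, 54% and 32% at the first mean, and over 99%, 99% and 88% at the second. The loss remains large.

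**Aim 2 may have more than one torque value per leg.** The protocol (Secondary Aim) tests at 60 and 180 °/sec. A subject intercept suffices only with one value per leg, so each speed needs its own model.

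**Conclusion.** The concern holds and should be fixed before analysis. That the model sentences omit the powered term and name no test is a matter of text, and is certain for both aims. The missing biopsy effect concerns Aim 1 only and is conditional on what fiber number means.

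The percentages depend on the unstated split s, the assumed fibre counts per leg, balanced data, and osteoarthritis before/after clusters standing in for leg clusters. Part (a) also assumes the stated powers are right and that NMES leaves the other leg unchanged. There is no inflation at s = 0 and no power loss at s = 1. In between, MHC I CSA is badly affected under either reading: even at s = 0.1 the literal model has 12–13% power, and the interaction without a biopsy term rejects 29–42% of the time under the null. Tension is the least affected.

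**What to change.** **Aim 1.** Replace the model sentence with, for example: *Fixed effects are group, leg and group × leg; random intercepts are subject and leg within subject (biopsy); the single fibre is the residual. The primary test of NMES is group × leg, two-sided 5%, with Kenward–Roger degrees of freedom (about 18 at 10 per group).* Satterthwaite would also serve; the SAP should name one. With balanced data this equals a two-sample t-test on each subject's injured-minus-uninjured difference in mean fibre value. If fiber number was meant to index the biopsy, say so.

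**Aim 2.** Add group × leg, keep subject as the random effect, name group × leg as the test, and fit each torque speed separately.

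**Also** state whether fibre counts are per leg or per patient, and correct the reference numbered 21.

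**Cost.** SAP wording only; no new patients or data. Aim 1 interaction standard errors will be wider than without a biopsy effect, but valid. Aim 2 gives up one degree of freedom.
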